## 5.3 Phase II

Having established an MTD in phase I, phase II will be conducted to assess the efficacy and toxicity of carfilzomib in combination with PLD and dexamethasone in participants with relapsed or refractory multiple myeloma.

Seventeen participants will be treated at the MTD of carfilzomib in combination with PLD and dexamethasone. Participants treated in phase 1 at the MTD will be counted as part of the phase two accrual. If  $\leq 5$  successes (CR, VGPR, or PR) are observed, we will

consider this regimen ineffective in this participant population and will not recommend further testing.

#### **5.4 Requirements to Start Treatment (Cycle 1 Day 1)**

- ALT (SGPT) and AST (SGOT) < 2.5 x the upper limit of the institutional normal value (ULN).
- Total bilirubin  $\leq$  1.5 x ULN.
- ANC  $\geq$  0.5.
- Platelets  $\geq$  25,000.
- Creatinine clearance > 15 ml/min using Cockcroft-Gault formula (See Appendix C).

#### **5.5 Accrual**

The anticipated accrual rate for the phase I portion is 1 participant per calendar month, with a total accrual time of two years. The anticipated accrual rate for the phase II portion is 1-2 participants per calendar month, with a total accrual time of one year.

### **6.0 DOSE-LIMITING TOXICITIES/DOSE MODIFICATIONS**

#### **6.1 Definition of Dose-limiting Toxicity**

Participants will be evaluated for toxicity according to the Common Terminology Criteria for Adverse Events (CTCAE) of the National Cancer Institute (NCI) version 4.0. A DLT is defined as any of the below treatment emergent toxicities with attribution to one or both of the study drugs that occur during Cycle 1. Toxicities that occur in subsequent cycles will be handled through dose modifications (Section 6.2) but will not be considered DLTs or figure into the definition of MTD.

As the study uses a lead in dose of 20mg/m^2 of Carfilzomib for days 1 and 2 for all dose levels, toxicity that requires dose reduction or doses to be held prior to Day 8 of cycle 1 will not be considered a DLT, but will result in the participant being ineligible for MTD analysis. The participant may remain on protocol therapy at the PI's discretion, and an additional participant will be enrolled into the cohort for MTD analysis.

In Phase 1, inability to receive >80% of Carfilzomib doses and 100% of PLD doses in Cycle 1 for reasons other than toxicity will result in the participant being ineligible for MTD analysis. The participant may remain on protocol therapy at the PI's discretion, and an additional participant will be enrolled into the cohort for MTD analysis.

Inability to receive >80% of Dex doses for reasons other than toxicity will result in the participant being ineligible for MTD analysis (only patients treated in part 2).

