## 5.0 TREATMENT PLAN

### 5.1 Overview

Carfilzomib will be administered on Days 1, 2, 8, 9, 15, and 16 during Cycles 1 through 6, and on Days 1, 8, 15, and 22 beginning on Cycle 7 until disease progression or clinical relapse. Participants treated prior to approval of amendment 1, will have carfilzomib administered on Days 1, 2, 8, 9, 15, and 16 during Cycles 1 and 2 and on Days 1, 8, 15, and 22 beginning on Cycle 3. PLD will be administered on Day 8 during Cycles 1 through 6. Dexamethasone will be administered on the same schedule as carfilzomib (patients treated in part 2 of phase 1 or phase 2).

Participants that have PLD or dexamethasone discontinued for toxicity may remain on study to receive the planned study drug doses at the PI's discretion.

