### 6.3 Missed Doses

Missed doses will not be replaced during a cycle. Doses can be adjusted by +/- 2 days to allow for holidays, travel issues, etc. Additional adjustments may be granted at the PI's discretion. Everything possible should be done to prevent adjustments from in the study schedule during Cycle 1.

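### The Cycle 1 exposure rule in section 6.1 makes no exception for a participant with a DLT, so a DLT combined with a non-toxicity dose shortfall drops out of the MTD count

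*Combined protocol and SAP*

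**What the plan says.** Section 6.1 sets a minimum Cycle 1 exposure for the MTD analysis. The condition is "In Phase 1, inability to receive >80% of Carfilzomib doses and 100% of PLD doses in Cycle 1 for reasons other than toxicity". The consequence is that it "will result in the participant being ineligible for MTD analysis. The participant may remain on protocol therapy at the PI's discretion", and that "an additional participant will be enrolled into the cohort for MTD analysis". For Part 2 there is a parallel sentence: "Inability to receive >80% of Dex doses for reasons other than toxicity will result in the participant being ineligible for MTD analysis". That sentence does not mention replacement.

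Four other provisions bear on the point:

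- **DLT definition (6.1).** "A DLT is defined as any of the below treatment emergent toxicities with attribution to one or both of the study drugs", occurring in Cycle 1. No minimum exposure is needed for an event to be a DLT.
- **Lead-in rule (6.1).** This is separate from the exposure rule: "toxicity that requires dose reduction or doses to be held prior to Day 8 of cycle 1 will not be considered a DLT". Such a participant is also ineligible and replaced.
- **Schedule (5.1, 6.3).** "Carfilzomib will be administered on Days 1, 2, 8, 9, 15, and 16 during Cycles 1 through 6", and PLD is given once per cycle, on Day 8. "Missed doses will not be replaced during a cycle".
- **Decision rules (5.2.1, 5.2.2).** Both count participants with a DLT. Neither sets an exposure condition, and neither says that a participant with a DLT stays evaluable after a shortfall.

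**The concern.** An exposure rule exists because a DLT-free cycle on too little drug is weak evidence that the dose is tolerable. The argument does not run the other way. A drug-attributed DLT on less than the planned dose is still evidence against that dose. Section 6.1 treats the two cases alike and removes both.

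Two situations show the gap. In the first, the Day 8 PLD dose is lost for logistical reasons and grade 4 thrombocytopenia follows on Day 15. In the second, a participant has a DLT on Day 9 and withdraws consent on Day 12, and the missed Day 15 and 16 doses are recorded as due to withdrawal. Section 8.1 lists withdrawal of consent separately from adverse events, so that coding is available. Section 6.1 names nobody independent to judge the reason for a shortfall, so it may be assigned with the DLT already known.

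Finding the MTD is the primary objective of both parts of phase I, and the MTD is the phase II dose. In a 3+3 design one participant can change the decision.

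**Working it through.** **The plan's own figures.** Six participants at each of four levels gives 4 × 6 = 24, the Part 1 maximum. Six at each of two levels gives 2 × 6 = 12, the Part 2 maximum. Both reproduce.

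**What triggers the rule.** Cycle 1 has six carfilzomib doses and one PLD dose.

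- One carfilzomib dose missed: 5/6 = 83.3%, above 80%, so the participant stays.
- Two missed: 4/6 = 66.7%, so the participant is removed if the reason is not toxicity.
- The single PLD dose missed: 0%, so the participant is removed on the same condition.

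In the second example above, Days 1, 2, 8 and 9 were given. That is 4/6, below the threshold.

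**Effect on one cohort.** Take 2 DLTs in 3, which stops escalation. Remove one DLT participant and the record is 1 in 2, with a replacement still to be observed. To escalate, the replacement must be DLT-free (giving 1 in 3) and so must the next three. At an assumed DLT rate of 0.40, with no further removals, that has probability 0.6⁴ = 0.13. A certain stop becomes about a 13% chance of escalating.

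**Effect on the escalation probability.** Under 5.2.1, with DLT rate p among evaluable participants:

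P(escalate) = (1−p)³ + 3p(1−p)² × (1−p)³

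Let d be the true DLT rate, a the non-toxicity shortfall rate among participants with a DLT, and b the rate among those without. The evaluable DLT rate is:

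- as written: d(1−a) / [d(1−a) + (1−d)(1−b)]
- if every DLT counts: d / [d + (1−d)(1−b)]

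The documents give none of d, a or b. With d = 0.40 and b = 0.10 assumed:

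| Case | Evaluable DLT rate | P(escalate) |
|---|---|---|
| As written, a = 0.05 | 0.38/0.92 = 0.413 | 0.29 |
| As written, a = 0.10 (unrelated to DLT) | 0.36/0.90 = 0.400 | 0.309 |
| As written, a = 0.20 | 0.32/0.86 = 0.372 | 0.357 |
| As written, a = 0.30 | 0.28/0.82 = 0.341 | 0.412 |
| Every DLT counts | 0.40/0.94 = 0.426 | 0.269 |

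The fair benchmark for bias is 0.309, the value at the true rate. Against it, the rule adds about 5 points at a = 0.20 and 10 points at a = 0.30. It adds nothing at a = 0.10 and subtracts about 2 points at a = 0.05.

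**Other DLT rates.** Suppose only DLT participants are removed (b = 0), with a between 5% and 30%. The chance of escalating then moves as follows:

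- d = 0.20: from 0.709 to between 0.726 and 0.816
- d = 0.33: from 0.434 to between 0.456 and 0.586
- d = 0.50: from 0.172 to between 0.187 and 0.291

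Across these cases the increase is about 1.5 to 15 points.

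**The case against.** A reader might infer that the rule removes any participant with a DLT who misses enough doses, and that it therefore biases the MTD upward. The documents support neither step.

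The rule is limited to shortfall for reasons other than toxicity. In phase I, section 6.2.1 requires the dose modifications to be followed directly in Cycle 1, and most listed DLTs lead to a hold under 6.2.2 and 6.2.3. Doses missed after a DLT will therefore usually be toxicity-driven, and the participant stays in the analysis. This weakens the second example. A participant on hold from Day 9 might have missed Days 15 and 16 anyway, so the recorded reason is at best ambiguous. The first example is less exposed to this objection, but section 6.3 allows a two-day window, further adjustment at the PI's discretion, and asks that schedule changes in Cycle 1 be avoided. Losing the only PLD dose to logistics should be uncommon.

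On bias, removing under-exposed participants regardless of DLT status leaves the evaluable DLT rate at its true value when shortfall is unrelated to DLT. The gap between 31% and 27% is then the conservatism of the alternative rule, not an error in the plan. If the misses of DLT participants are mostly classed as toxicity, a could even be below b, and the rule as written would lean conservative.

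Section 14.0 also has the PI review patient data before each escalation and report DLTs by cohort to the QASMC, so a DLT would not be hidden.

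All of this narrows the point, but the gap remains. Reporting a DLT does not make the participant evaluable under 6.1. Nothing in 5.2.1, 5.2.2 or 6.1 retains a participant who has both a DLT and a non-toxicity shortfall.

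**Conclusion.** The gap is real but narrow. Followed as written, section 6.1 discards an observed, drug-attributed DLT when the same participant also has a non-toxicity shortfall in carfilzomib, PLD or, in Part 2, dexamethasone. For carfilzomib and PLD it also orders a replacement.

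Upward bias in the MTD is conditional: it needs such shortfall to be more common among participants with a DLT than among those without. Withdrawal after a DLT is a plausible route, but the documents do not quantify it. At an assumed DLT rate of 40%, with shortfall of 10% without a DLT and 20-30% with one, the chance of escalating past a level is 36-41%, against 31% at the true rate. With equal shortfall in both groups there is no bias. How often the situation would arise cannot be derived from the documents.

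This is a should-fix: the frequency is probably low, but the consequence falls on the primary phase I objective and the repair is cheap.

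**What to change.** Add to section 6.1, so that it governs both the carfilzomib/PLD sentence and the dexamethasone sentence:

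> A participant with a Cycle 1 event that meets the DLT definition (other than toxicity before Day 8 covered by the lead-in sentence) is evaluable for MTD and counted as a DLT regardless of the number of carfilzomib, PLD or Dex doses received; the non-toxicity exposure rules exclude and replace only participants without a DLT.

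The parenthesis ties the new sentence to the existing lead-in rule and leaves that rule unchanged. The last clause also settles replacement for a dexamethasone shortfall, which 6.1 leaves open. The change concerns evaluability only and alters no dosing or treatment rule.

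The cost is one sentence in an amendment. It needs no extra participants and should mean fewer replacements. The downside is a slightly conservative DLT count, because DLT-free participants with a shortfall are still removed while those with a DLT are kept. In the 40% example with 10% shortfall in both groups, the chance of escalating falls from 31% to 27%.

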#### Hematologic DLTs

- $\geq$  Grade 4 thrombocytopenia

- $\geq$  Grade 4 neutropenia
- $\geq$  Grade 3 febrile neutropenia (fever  $\geq$  38.5 degrees C and ANC  $<$ 1000k/cumm)

#### Non-Hematologic DLTs

- $\geq$  Grade 2 neuropathy with pain
- $\geq$  Any grade 3 non-hematologic toxicity (excluding nausea, vomiting, diarrhea)
- $\geq$  Grade 3 nausea, vomiting, or diarrhea for  $>$  3 days despite maximal antiemetic/antidiarrheal therapy
- Any non-hematologic toxicity requiring a dose reduction within Cycle 1
- Inability to receive Day 1 dose of Cycle 2 due to drug-related toxicity persisting from Cycle 1 or drug-related toxicity newly encountered on Day 1 of Cycle 2
- Delay of  $>$  14 days in initiating Day 1 of Cycle 2 due to drug-related toxicity

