### 5.2.1 Dose Escalation Rule

Number of Participants with a DLT at a Dose Level	Escalation Decision Rule
0	Enter 3 participants at the next dose level.
1 out of 3	Enter 3 more participants at this dose level.  If none of the additional participants experiences a DLT, then proceed to the next dose level. If $\geq 1$ of the additional participants experiences a DLT, then dose escalation is stopped and the level below is declared the MTD.
$\geq 2$	Dose escalation is stopped. Enter 3 more participants at the next lower dose level if only 3 participants had previously been treated at that dose level.

Only after the last participant on at each dose level completes one cycle of treatment will the first participant in the next dose level be enrolled.

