### 5.2.2 Definition of Maximum Tolerated Dose

The maximum tolerated dose (MTD) is defined as the dose level immediately below the dose level at which 2 participants of a cohort (of 2 to 6 participants) experience dose limiting toxicity (DLT) during the first cycle of treatment. (See Section 6.0 for information on what constitutes a DLT.) Dose escalation will proceed until the MTD has been reached.

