## **6.2 Dosing Modifications**

### **6.2.1 Overview**

Dose modifications for hematologic and non-hematologic toxicities are summarized in sections 6.2.2 and 6.2.3 respectively. Participants who have treatment delayed for greater than four weeks should discontinue protocol therapy.

A maximum of 2 dose reductions of carfilzomib or Dex and 1 dose reduction of PLD will be allowed for each participant. More than two dose reductions of Dex or one dose reduction of PLD will require the agent be discontinued. Participants that permanently discontinue Dex or PLD due to toxicity can remain on study and receive the other planned study drug doses at the investigator's discretion. Participants requiring a third dose reduction of carfilzomib will have treatment discontinued.

If the participant tolerates the reduced dose for one cycle, the participant may be dose escalated to the study drug dose(s) prior to reduction at the discretion of the Investigator.

Dose modifications should be followed directly for Cycle 1 for all patients treated in the phase I portion of the study. In Cycles 2+ for patients treated in the phase I portion, and for any cycle for patients treated in the phase II portion, dose modifications and delays different from those stated in the protocol for management of toxicities will be permitted at the discretion of the Principal Investigator.

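### Section 6.1 counts a Cycle 2 Day 1 event as a DLT, but the Cycle-1-only sentences and the escalation gate make no room for it

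*Combined protocol and SAP*

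**What the plan says.** - **Section 6.1, general definition.** A DLT is any one of a list of toxicities "with attribution to one or both of the study drugs that occur during Cycle 1". For later cycles: "Toxicities that occur in subsequent cycles will be handled through dose modifications (Section 6.2) but will not be considered DLTs".
- **Section 6.1, non-hematologic list.** Two adjacent items concern the start of Cycle 2. One is "Inability to receive Day 1 dose of Cycle 2 due to drug-related toxicity persisting from Cycle 1", or because of toxicity that first appears on that day; no duration is given. The other is a delay of more than "14 days in initiating Day 1 of Cycle 2 due to drug-related toxicity".
- **Section 5.2.2.** The MTD is the level below the one at which two participants "experience dose limiting toxicity (DLT) during the first cycle of treatment".
- **Section 5.2.1.** On when enrolment may move up: "Only after the last participant on at each dose level completes one cycle of treatment will the first participant in the next dose level" enter the study. With three participants, no DLT means escalate, one means add three more, and two or more mean stop. If any of the three added participants has a DLT, escalation stops.
- **Section 7.1.4.** A cycle is 28 days.
- **Section 6.2.1.** For phase I participants from Cycle 2 on, "dose modifications and delays different from those stated in the protocol for management of toxicities will be permitted" at the Principal Investigator's discretion.
- **Section 6.1, Part 2.** A dexamethasone rule has been added: "Inability to receive >80% of Dex doses for reasons other than toxicity will result in the participant being ineligible for MTD analysis". The attribution phrase still speaks of one or both drugs.

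**The concern.** DLT counts set the MTD, and the MTD is the phase II dose. Three parts of the rule do not fit together.

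1. Toxicity that is new on Cycle 2 Day 1 is a DLT under one sentence of 6.1. It is not a DLT under another sentence of 6.1, or under 5.2.2.
2. The gate in 5.2.1 can be satisfied before the Cycle 2 Day 1 criterion can be assessed. Followed as written, it allows the next level to open while a DLT at the current level is still undetermined.
3. The 14-day bullet has no work to do if any toxicity-related missed Cycle 2 Day 1 already counts. A reader who assumes that every bullet has a purpose may take 14 days as the threshold and stop counting shorter delays.

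**Working it through.** The plan states no figure on this point, so there is none to reproduce. The check is a day count and an enumeration of the decision table.

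**Day count** (28-day cycle, Section 7.1.4)
- Cycle 1 ends on Day 28, which is when the 5.2.1 gate can be met.
- Cycle 2 Day 1 is 28 + 1 = Day 29. The inability criterion can first be assessed 29 − 28 = 1 day after the gate.
- A delay of more than 14 days is first met on 29 + 15 = Day 44, which is 44 − 28 = 16 days after the gate. This matters only if the 14-day bullet is taken to govern.

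**Do the Cycle 1 limits catch the criterion?**
- Toxicity that persists from Cycle 1 arose in Cycle 1, so it can be squared with the general sentences.
- Toxicity first seen on Day 29 cannot. It belongs to a subsequent cycle, yet it is listed as a DLT. The list item works as a specific exception, but neither general sentence refers to it.

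**Decision for three participants** (Section 5.2.1). Delay-only means that the participant's sole event is a toxicity delay of 1-14 days.

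| Other DLTs | Delay-only | Literal text | 14-day reading |
|---|---|---|---|
| 0 | 0 | escalate | escalate |
| 0 | 1 | expand | escalate |
| 0 | 2 or 3 | stop | escalate |
| 1 | 0 | expand | expand |
| 1 | 1 or 2 | stop | expand |
| 2 or 3 | any | stop | stop |

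Escalation is possible only in Part 1, at a level with a higher one above it. Part 2 has only a starting level and one below, so the gate problem does not arise there.

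**Which toxicities are affected?** Only those that hold dosing without already being a DLT. An example is a first episode of grade 2 stomatitis or palmar-plantar erythrodysesthesia, for which Section 6.2.3 says to hold all drugs and then resume at the same dose.

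**Illustration only.** The documents give no rates. Let a be the assumed probability of another DLT, d that of a delay-only event, and n = 1 − a − d. The two readings disagree in a first cohort of three with probability 3dn² + (3d²n + d³) + 3a(2dn + d²).
- At a = 0.10 and d = 0.05: 0.108 + 0.007 + 0.026 = 0.141.
- For a from 0.05 to 0.20, the total is 0.056-0.059 at d = 0.02 and 0.259-0.270 at d = 0.10.

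These values show only how the result depends on the assumed rates. They do not measure the size of the problem.

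**The case against.** **The text gives one answer.** Any single item suffices, so a toxicity-related missed Cycle 2 Day 1 is a DLT whatever its length. Nothing makes the 14-day bullet a limit on that item. This stands. A reader might infer that 6.1 contradicts itself on the threshold, but the documents show a redundant bullet that invites a misreading.

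**The gate is backed up elsewhere.** The 5.2.1 table acts on DLT counts. Section 14.0 has the Principal Investigator review all data at least monthly, or before each escalation if that is sooner. Both help, but neither requires Cycle 2 Day 1 status to be settled before the next level opens. On the literal text the gap is one day.

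**The 16-day gap is a special case.** This also stands. It needs the non-literal reading, and Section 8.1 allows removal once drug has been held for more than two continuous weeks for an adverse event. A hold that began on Day 15 would pass that limit at about Day 30, so Day 44 is relevant only if no Cycle 1 dose was already on hold.

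**Holding at Day 29 may not be mandatory.** Section 6.2.1 allows departures from the hold rules from Cycle 2 on, so the stomatitis example need not end in a missed dose. This lowers the likely frequency. It does not settle how a missed dose is classified.

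**Dexamethasone.** A reader might infer that the attribution phrase excludes dexamethasone-only toxicity in Part 2. The documents do not support that. Section 6.2.1 groups dexamethasone with PLD and speaks of the other planned study drug doses, so dexamethasone can be the one drug in the phrase. The Cycle 2 Day 1 items say only that the toxicity is drug-related. The wording is stale and does not clearly exclude such events.

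**Conclusion.** The point holds as a correction to the rules that set the MTD. One DLT criterion falls on Day 29 or later. Two sentences that confine DLTs to the first cycle do not acknowledge it, and the escalation gate can be met on Day 28 without it. On the literal text the timing gap is one day.

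The 14-day bullet adds nothing on that text. If it were read as a threshold, the 3+3 decision would change for any first cohort that has at least one delay-only participant and fewer than two other DLTs. In the simplest case, one such participant in three, the change is from expand to escalate. This follows from the decision table alone. Its frequency cannot be derived from the documents, and no probability should be quoted as the magnitude.

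**What to change.** 1. **Section 6.1, list.** Keep one criterion: any drug-related inability to receive Cycle 2 Day 1 as scheduled, whether the toxicity persists from Cycle 1 or is new that day. State that the ±2 day allowance in Section 6.3 covers scheduling reasons and not toxicity. Delete the 14-day bullet.
2. **Sections 6.1 and 5.2.2.** Name this criterion as the exception to the Cycle-1-only sentences.
3. **Section 5.2.1.** Open the next level only when every participant evaluable for the MTD at the current level has received Cycle 2 Day 1 or has had DLT status determined.
4. **Tidying only.** For Part 2, let the attribution phrase read *one or more of the study drugs*.

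The cost is a wording amendment and about one extra day before a level opens, longer only if a participant is delayed. Planned phase I accrual is one participant per month (Section 5.5). Short toxicity delays would count as DLTs, which can lower the MTD, but the literal text already requires this. If the sponsor wants to tolerate delays of up to 14 days, that is a less protective design and should be written as a deliberate change.
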